7.1.3. Severity of an Adverse Event

The severity of each adverse event must be recorded as 1 of the following:

Mild: No limitation of usual activities

Moderate: Some limitation of usual activities

Severe: Inability to carry out usual activities

7.1.4. Relationship of an Adverse Event to the IMP

The relationship of an adverse event to the IMP is characterized as follows:

Term	Definition	Clarification
No reasonable possibility (not related)	This category applies to adverse events that, after careful consideration, are clearly due to extraneous causes (disease, environment, etc) or to adverse events that, after careful medical consideration at the time they are evaluated, are judged to be unrelated to the IMP.	
The relationship of an adverse event may be considered “no reasonable possibility” if it is clearly due to extraneous causes or if at least 2 of the following apply:
 
 • It does not follow a reasonable temporal sequence from the administration of the IMP. • It could readily have been produced by the patient’s clinical state, environmental, or toxic factors, or other modes of therapy administered to the patient. • It does not follow a known pattern of response to the IMP. • It does not reappear or worsen when the IMP is re-administered.
Reasonable possibility (related)	This category applies to adverse events for which, after careful medical consideration at the time they are evaluated, a connection with the administration of IMP cannot be ruled out with certainty.	
The relationship of an adverse event may be considered “reasonable possibility” if at least 2 of the following apply:
 
 • It follows a reasonable temporal sequence from administration of the IMP. • It cannot be reasonably explained by the known characteristics of the patient’s clinical state, environmental or toxic factors, or other modes of therapy administered to the patient. • It disappears or decreases on cessation or reduction in dose. There are important exceptions when an adverse event does not disappear after discontinuation of the IMP, yet an IMP relationship clearly exists. • It follows a known pattern of response to the IMP.

7.1.5. Serious Adverse Events

An additional blood sample for the measurement of IMP concentration should be collected, if possible, from each patient experiencing a serious adverse event leading to discontinuation of IMP at any time during the study. If study center personnel are unable to obtain a blood sample in a timely fashion, this should be discussed with the medical monitor to determine whether the sample still needs to be obtained.

For recording of serious adverse events, the study period is defined for each patient as the time period from signature of the informed consent/assent form to the end of the follow-up period, as defined in Section 7.1.2. If the investigator becomes aware of serious adverse events occurring in a patient after the end of the follow-up period, the serious adverse events should be reported to the sponsor following the procedures described in Section 7.1.5.3.1.

7.1.5.1. Definition of a Serious Adverse Event

A serious adverse event is an adverse event occurring at any dose that results in any of the following outcomes or actions:

- results in death
- is a life-threatening adverse event (ie, the patient was at risk of death at the time of the event); it does not refer to an event which hypothetically might have caused death if it were more severe.
- requires inpatient hospitalization or prolongation of existing hospitalization, which means that hospital inpatient admission or prolongation of hospital stay were required for treatment of an adverse event, or that they occurred as a consequence of the event.

Hospitalizations scheduled before the patient signed the informed consent form will not be considered serious adverse events, unless there was worsening of the preexisting condition during the patient's participation in this study.

- results in persistent or significant disability/incapacity (refers to a substantial disruption of one's ability to conduct normal life functions)
- is a congenital anomaly/birth defect
- an important medical event that may not result in death, be life-threatening, or require hospitalization, but may jeopardize the patient and may require medical intervention to prevent one of the outcomes listed in this definition.

Examples of such events are intensive treatment in an emergency room or at home for allergic bronchospasm; blood dyscrasias or convulsions that do not result in hospitalization; or the development of drug dependency or drug abuse. Note: Any suspected transmission of an infectious agent via a medicinal product is considered an important medical event.

All occurrences of possible drug-induced liver injury that meet Hy's law criteria, defined as **all** of the below, must be reported by the investigator to the sponsor as a serious adverse event:

- alanine aminotransferase (ALT) or aspartate aminotransferase (AST) increase of $>3 \times$ the upper limit of normal (ULN)
- total bilirubin increase of $>2 \times$ ULN
- absence of initial findings of cholestasis (ie, no substantial increase of alkaline phosphatase [ALP])

An adverse event that does not meet any of the criteria for seriousness listed above will be regarded as a nonserious adverse event.

7.1.5.2. Expectedness

A serious adverse event that is not included in the adverse reaction section of the relevant reference safety information (RSI) by its specificity, severity, outcome, or frequency is considered an unexpected adverse event. The RSI for this study is the IB.

A serious adverse event that is not included in the listing of adverse reactions in the RSI by its specificity, severity, outcome, or frequency is considered an unexpected adverse event.

The sponsor's GPSP will determine the expectedness for all serious adverse events.

For the purpose of SUSAR reporting, the version of the IB at the time of occurrence of the SUSAR applies.

7.1.5.3. Reporting a Serious Adverse Event

7.1.5.3.1. Investigator Responsibility

To satisfy regulatory requirements, all serious adverse events that occur during the study, regardless of judged relationship to administration of the IMP, must be reported by the investigator according to the instructions provided on the serious adverse event form. The event must be reported within 24 hours of when the investigator learns about it. Completing the Serious Adverse Event Form and reporting the event must not be delayed, even if not all the information is available. The investigator does not need to actively monitor patients for adverse events once this study has ended.

Serious adverse events occurring to a patient after the last administration of IMP of that patient has ended should be reported to the sponsor if the investigator becomes aware of them.

The serious adverse event form should be sent to the local safety officer (LSO) or designee (a contract research organization in a country without a sponsor LSO) (contact information is in the Clinical Study Personnel Contact Information section); the LSO will forward the report to the sponsor's GPSP.

The following information should be provided to record the event accurately and completely:

- study number
- investigator and investigational center identification
- patient number
- onset date and detailed description of adverse event
- investigator's assessment of the relationship of the adverse event to the IMP (no reasonable possibility, reasonable possibility)

Additional information includes:

- age and sex of patient
- date of first dose of IMP
- date and amount of last administered dose of IMP
- action taken
- outcome, if known
- severity
- explanation of assessment of relatedness

- concomitant medication (including doses, routes of administration, and regimens) and treatment of the event
- pertinent laboratory or other diagnostic test data
- medical history
- results of dechallenge/rechallenge, if known
- for an adverse event resulting in death:
 - cause of death (whether or not the death was related to IMP)
 - autopsy findings (if available)

Each report of a serious adverse event will be reviewed and evaluated by the investigator and the sponsor to assess the nature of the event and the relationship of the event to the IMP, study procedures, and to underlying disease.

Additional information (follow-up) about any serious adverse event unavailable at the initial reporting should be forwarded by the investigator within 24 hours of when it becomes known to the same address as the initial report.

For all countries, the sponsor's GPSP will distribute the Council for International Organizations of Medical Sciences (CIOMS) form/Extensible Markup Language (XML) file to the LSO/Syneos Health for submission to the competent authorities, IEC/IRBs, and investigators, according to regulations. The investigator must ensure that the IEC/IRB is also informed of the event, in accordance with national and local regulations.

Blinding will be maintained for all study personnel. Therefore, in case of a SUSAR, only the LSO/Syneos Health will receive the unblinded report for regulatory submission; the others will receive a blinded report.

Note: Although pregnancy is not a serious adverse event, the process for reporting a pregnancy is the same as that for reporting a serious adverse event, but using the pregnancy form (see Section 7.3).

7.1.5.3.2. Sponsor Responsibility

If a serious unexpected adverse event is believed to be related to the IMP or study procedures, the sponsor will take appropriate steps to notify all investigators participating in sponsored clinical studies of TEV-50717 and the appropriate competent authorities (and IEC/IRB, as appropriate).

In addition to notifying the investigators and regulatory authorities (and IEC/IRB, as appropriate), other action may be required, including the following:

- altering existing research by modifying the protocol
- discontinuing or suspending the study
- modifying the existing consent form and informing current study participants of new findings

- modifying listings of expected toxicities to include adverse events newly identified as related to TEV-50717

7.1.6. Protocol-Defined Adverse Events of Special Interest

No protocol-defined adverse events of special interest were identified for this study.

7.1.7. Withdrawal Due to an Adverse Event

Any patient who experiences an adverse event may be withdrawn from the study or from study treatment at any time at the discretion of the investigator or sponsor. If a post-baseline QTcF value >500 msec or change from baseline >60 msec is found, the investigator should repeat the ECG assessment twice and compare the average of the 2 pre-treatment QTcF values (baseline and screening) to the average of the 3 post-baseline QTcF values. The IMP must be stopped for any confirmed post-baseline QTcF value >500 msec or increase from baseline >60 msec. If a patient is withdrawn wholly or in part because of an adverse event, both the adverse events page and termination page of the CRF will be completed at that time.

In addition, a blood sample should be obtained for the measurement of IMP concentrations, if possible. The patient will be monitored at the discretion of the investigator (eg, until the event has resolved or stabilized, until the patient is referred to the care of a health care professional, or until a determination of a cause unrelated to the IMP or study procedure is made). The investigator must inform the clinical project physician/clinical leader as soon as possible of any patients who are being considered for withdrawal due to adverse event(s). Additional reports must be provided when requested.

If a patient is withdrawn from the study for multiple reasons that include adverse events, the termination page of the CRF should indicate that the withdrawal was related to an adverse event. An exception to this requirement will be the occurrence of an adverse event that, in the opinion of the investigator, is not severe enough to warrant discontinuation but that requires the use of a prohibited medication, thereby requiring discontinuation of the patient. In such a case, the reason for discontinuation would be need to take a prohibited medication, not the adverse event.

7.1.8. Protocol Deviations Because of an Adverse Event

If a patient experiences an adverse event or medical emergency, deviations from the protocol may be allowed on a case-by-case basis. To ensure patient safety, after the event has stabilized or treatment has been administered (or both), the investigator or other physician in attendance must contact the physician identified in the Clinical Study Personnel Contact Information section of this protocol as soon as possible to discuss the situation. The investigator, in consultation with the sponsor, will decide whether the patient should continue to participate in the study.

7.2. Psychometric Rating Scales

Site-administered safety scales include the MINI Kid and C-SSRS, and self-administered safety scales include CDI-2.

7.2.1. Mini International Neuropsychiatric Interview for Children and Adolescents

Select MINI Kid modules are administered at screening only. Children 13 years of age and under may be interviewed separately or jointly with the caregiver/adult as appropriate or defined by the scale. For children over 13 years of age, caregiver/adult involvement is strongly encouraged. Questions should be directed to the child, but the caregiver/adult should be encouraged to add relevant information.

The MINI Kid is a short questionnaire to be administered by a trained clinician. The MINI Kid assesses symptoms of psychiatric disorders as outlined in the International Classification of Diseases-10 and the DSM in children 6 to 17 years of age by self-report. For children under 13 years old, the patient may be interviewed separately or jointly with the caregiver/adult as appropriate or defined by the scale, and the caregiver/adult is encouraged to participate when needed. The MINI Kid version 6 is composed of 24 modules overall, and questions are largely yes-or-no questions. The current study will focus on 8 modules: Major Depressive Episode (Module A), (Hypo) Manic Episode (Module D), OCD (Module J), Alcohol Dependence/Abuse (Module L), Substance Dependence/Abuse (Non-alcohol; Module M), ADHD (Module O), Conduct Disorder (Module P), and Psychotic Disorders and Mood Disorders with Psychotic Features (Module R).

A reference sample is provided in [Appendix C](#).

7.2.2. Columbia-Suicide Severity Rating Scale

The C-SSRS children's baseline/screening scale assesses past and current suicidal ideation and behaviors to determine suicide risk and is administered at screening. The C-SSRS children's SLV scale is administered at baseline and at weeks 2, 4, 6, 9, 12, and 13. Children 13 years of age and under may be interviewed separately or jointly with the caregiver/adult as appropriate or defined by the scale. For children over 13 years of age, caregiver/adult involvement is strongly encouraged. Questions should be directed to the child, but the caregiver/adult should be encouraged to add relevant information. The C-SSRS is an interview by trained study personnel.

Suicidal ideation

- Patients with a positive C-SSRS suicidal ideation score on either items 1 or 2 or a change on the CDI-2 Parent or Self-Report Profiles consistent with increasing depressive symptoms must be 1) discussed with the medical monitor, 2) re-evaluated within 2 to 3 days in a clinic visit, and 3) treated according to the investigator's medical judgment. Consultation with a child and adolescent psychiatrist or licensed child/adolescent mental health provider is advised, followed by close ongoing monitoring.
- If patients endorse or report a C-SSRS suicidal ideation level of 3, 4, or 5, subjects will be evaluated immediately by the study investigator and referred for psychiatric evaluation. The medical monitor will be immediately consulted. If it is determined by the investigator, after consultation with the medical monitor and the consulting psychiatrist, that exposure to the IMP may have contributed to this change in C-SSRS and/or increased depressive symptoms, IMP will be immediately discontinued and the patient terminated from the study. In cases where it is determined that IMP did not contribute to changes in depression or suicidality, the investigator will consult with the medical

monitor, the consulting psychiatrist, and/or sponsor to determine whether the patient should continue in the study.

Suicidal behavior

- Actual attempt:

If patients report any suicidal behavior that is an actual attempt as assessed in the C-SSRS, they will be evaluated immediately by the study investigator, referred for psychiatric evaluation, and terminated from the study.

- Interrupted attempt, aborted attempt, or Preparatory Acts or Behavior:

If patients report any suicidal behavior that is interrupted, aborted, or preparatory as assessed in the C-SSRS, they will be evaluated immediately by the study investigator and referred for psychiatric evaluation. In cases where it is determined in the psychiatric evaluation that IMP did not contribute to changes in suicidal behavior, the investigator will consult with the medical monitor, the consulting psychiatrist, and/or sponsor to determine whether the patient should continue in the study.

A reference sample is provided in [Appendix E](#).

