7.9. Assessment of Suicidality

TEV-50717 is considered to be CNS-active. In addition, there have been some reports of suicidal ideation or behavior as reported in the product label when it has been given to some patients with certain conditions. The sponsor considers it important to monitor for such events before and during this clinical study.

Some CNS-active IMPs may be associated with an increased risk of suicidal ideation or behavior when given to some patients with certain conditions. Although this IMP or other similar medicinal products in this class have not been shown to be associated with an increased risk of suicidal thinking or behavior when given to this study population, the sponsor considers it important to monitor for such events before or during this clinical study.

The study population being administered TEV-50717 should be monitored appropriately and observed closely for suicidal ideation and behavior or any other unusual changes in behavior. Consideration should be given to discontinuing TEV-50717 in participants who experience signs of suicidal ideation or behavior and detailed recommendations are provided in Section [7.2.2](#).

Baseline assessment of suicidal ideation and behavior and treatment-emergent suicidal ideation and behavior will be assessed during the study using the C-SSRS described in Section [7.2.2](#).

Depression and Suicidality as an Adverse Event

Families and caregivers of subjects in Study 30046 will be instructed to monitor patients for any changes in or new onset of depressive symptoms; unusual changes in mood, cognition, or behavior; or onset of and/or changes in suicidal ideation or behavior, and to report such symptoms immediately to the study investigator. Telephone contacts and clinic visits also allow opportunities for investigators to assess adverse events.

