If a relevant change in status is identified, patients will be seen immediately for an unscheduled visit by the study investigator and discussed with the medical monitor. The patient will be referred for further psychiatric evaluation if there is any suspected suicidal ideation with any level of intent, suicidal behavior, or clinical findings suggesting that the patient may be dangerous to self or others, and/or experiencing depression. The investigator will record these symptoms as an adverse event of depression and/or suicidality. If it is determined by the investigator, after consultation with the medical monitor and the consulting psychiatrist, that exposure to the IMP may have contributed to the adverse event of depression or suicidality, IMP will be immediately discontinued and the patient will be terminated from the study. Follow up

with a pediatric psychiatrist or licensed child and adolescent mental health clinician will be arranged.

In cases where it is determined that IMP did not contribute to the adverse event of depression or suicidality, the investigator will consult with the medical monitor and/or sponsor to determine whether the patient should continue in the study.

A reference sample is provided in [Appendix E](#).

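### After an actual suicide attempt judged unrelated to IMP, Section 7.2.2 requires termination but Section 7.9 leaves continuation to consultation

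*Protocol*

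**What the plan says.** Protocol Section 7.2.2 sorts suicidal behavior into two groups. The first is "any suicidal behavior that is an actual attempt as assessed in the C-SSRS"; for these patients the rule is that "they will be evaluated immediately by the study investigator, referred for psychiatric evaluation, and terminated from the study". No condition on relation to IMP is attached. The second group is interrupted attempts, aborted attempts and preparatory acts. Here the section opens a route to possible continuation: "In cases where it is determined in the psychiatric evaluation that IMP did not contribute to changes in suicidal behavior", the investigator consults on whether the patient stays. Ideation at levels 3 to 5 has a similar route. Of these categories, only the actual attempt has none.

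Section 7.9 contains a separate procedure for depression and suicidality as adverse events. Families are told to watch for "onset of and/or changes in suicidal ideation or behavior, and to report such symptoms immediately to the study investigator". When a relevant change is found, "patients will be seen immediately for an unscheduled visit by the study investigator and discussed with the medical monitor". Psychiatric referral follows "if there is any suspected suicidal ideation with any level of intent, suicidal behavior, or clinical findings" pointing to danger or depression, and the event is recorded as an adverse event of depression and/or suicidality. If IMP may have contributed, IMP stops at once and the patient is terminated. Otherwise: "In cases where it is determined that IMP did not contribute to the adverse event of depression or suicidality, the investigator will consult". That consultation is with the medical monitor and/or sponsor and concerns whether the patient should continue. An actual attempt is not excepted.

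Section 7.9 refers to 7.2.2 twice before that procedure. One sentence, whose closing reference is to 7.2.2, reads "Consideration should be given to discontinuing TEV-50717 in participants who experience signs of suicidal ideation or behavior and detailed recommendations are provided in Section". The other says that baseline and treatment-emergent suicidal ideation and behavior are assessed in the study with the C-SSRS of Section 7.2.2.

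**The concern.** The two sections give different instructions for the same event, an actual attempt judged unrelated to IMP. One prescribes the outcome; the other leaves it open. The difference matters most when the attempt comes to light outside a C-SSRS assessment, because the 7.2.2 rule is worded around what the C-SSRS shows, whereas 7.9 starts from a family report or clinical contact.

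The patients are children aged 6 to 16 receiving a drug that Section 7.9 itself describes as CNS-active, and a previous actual attempt excludes a child from entry (Section 4.2, criterion f). A site that follows 7.9 literally could keep such a child on blinded IMP after an attempt. The required consultation lowers that risk, but it does not tell the medical monitor or the sponsor which section binds them.

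**Working it through.** The plan states no figure to reproduce. The check sets the rules side by side and then measures how long the gap could last.

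**1. The same event under each section** (actual attempt, IMP judged not to have contributed)

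| | Section 7.2.2 | Section 7.9 |
|---|---|---|
| Trigger | Actual attempt, as assessed in the C-SSRS | Suicidal behavior recorded as an adverse event, however reported |
| Role of causality | None | Decides the branch |
| Outcome | Terminated from the study | Consult on whether to continue |

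Consulting and then terminating satisfies both columns. Consulting and then continuing satisfies 7.9 but, once the attempt is assessed in the C-SSRS, breaches 7.2.2. So 7.9 permits an outcome that 7.2.2 forbids.

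**2. Does any text rank the sections?** The first pointer in 7.9 asks for consideration of stopping the drug and says where detail can be found; it does not say that 7.2.2 prevails. The second names the instrument and its section but not when the C-SSRS must be done. The closing paragraph of 7.9, which sets the outcome when IMP did not contribute, refers to neither.

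**3. Is the C-SSRS required when the attempt is first seen?** No. Section 3.13.5 lists the Since Last Visit C-SSRS among the assessments left to the investigator's discretion at an unscheduled visit, and Table 1 footnote j says the same. The 7.9 steps can therefore be completed before 7.2.2 is triggered.

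**4. How long could that last?** Section 7.2.2 schedules the Since Last Visit C-SSRS at baseline and weeks 2, 4, 6, 9, 12 and 13. The nominal days are 1, 14, 28, 42 and 63 (protocol Table 1), then 84 (SAP Table 2). IMP stops at week 12, so only intervals up to day 84 count. Interval = day of next assessment − day of previous assessment:

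- Baseline to week 2: 14 − 1 = 13 days
- Week 2 to 4: 28 − 14 = 14 days
- Week 4 to 6: 42 − 28 = 14 days
- Week 6 to 9: 63 − 42 = 21 days
- Week 9 to 12: 84 − 63 = 21 days

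The longest nominal delay is thus about two weeks during titration and three weeks after week 6, for an attempt just after a scheduled visit. At weeks 6 and 9 patients receive three weeks of IMP (Section 5.1), so supply need not end sooner. The ±3-day visit window can move these figures slightly.

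**5. Does Section 4.4 settle it?** No. It lists 8 events (a to h) that give the investigator a right to withdraw a patient; none is a suicide attempt. Its closing sentence refers to 5 sections (3.7, 3.11, 3.13.4, 5.4, 7.1.7), neither 7.2.2 nor 7.9 among them. Items b (adverse events) and d (health or well-being) already allow withdrawal after an attempt, but do not require it.

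**The case against.** The strongest reply is that the intended rule can be recovered from the text. Section 7.2.2 is the specific rule and 7.9 the general one; 7.9 sends the reader to 7.2.2 both for detail and for the instrument; and the Amendment 04 summary (Section 17.4) shows that both texts were added together, for the same stated reason. An attempt reported by a family is treatment-emergent suicidal behavior, so on this reading it should be assessed with the C-SSRS and then fall under the termination rule.

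The harm also needs several things at once: an actual attempt; a finding that IMP did not contribute, when even possible contribution already means termination; no C-SSRS at the unscheduled visit; and a medical monitor or sponsor who chooses continuation. Meanwhile 7.9 requires an immediate visit, discussion with the medical monitor and psychiatric referral, and an attempt that meets the seriousness criteria is reported within 24 hours (Section 7.1.5.3.1).

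Most of this stands. It makes termination the likely intent and the event improbable. It does not remove the conflict, because intent has to be inferred: neither pointer sets the timing of the C-SSRS or says which section governs.

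Three stronger readings are tempting, and the documents do not support them. A reader might infer that no site can comply with both sections; consulting and then terminating does. A reader might infer that 7.9 lets a child stay on IMP for the rest of the trial; the next scheduled Since Last Visit C-SSRS should capture the attempt and bring 7.2.2 into force. A reader might treat the silence of 4.4 as a defect in its own right; 4.4 is permissive and already allows withdrawal.

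**Conclusion.** Wrong as written, at low severity. For an actual attempt judged unrelated to IMP, the last paragraph of 7.9 leaves open an outcome that 7.2.2 rules out. The practical exposure is a child kept on blinded IMP, nominally for up to two to three weeks, when the attempt is first reported between scheduled visits.

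This rests on three assumptions: that the investigator uses the discretion in Section 3.13.5 not to administer the C-SSRS at the unscheduled visit; that the consultation ends in continuation; and that the next scheduled C-SSRS records the attempt. The documents give no attempt rate, so no expected number of cases can be calculated. Sample size, power, type I error and the primary analysis are unaffected.

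Confidence is high that the two texts differ. That says nothing about how likely a site is to act on the difference.

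**What to change.** Add one clause to the closing paragraph of Section 7.9, which covers cases where IMP did not contribute: *except for an actual attempt, however it comes to light, for which the patient is terminated from the study (Section 7.2.2)*. The words *however it comes to light* close the gap for attempts reported outside a C-SSRS assessment, so the schedule of assessments can stay as it is.

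A cross-reference to 7.2.2 in Section 4.4, in the way item c already refers pregnancy to Section 7.3, would help readers. It is optional and would not by itself create a mandatory rule.

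Make the change in the next protocol amendment. Under Section 11.1.1 a written amendment normally needs prior ethics committee and, where applicable, competent authority approval, so a stand-alone amendment is not warranted. No procedure, visit or data item is added.
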